## 2. STUDY OBJECTIVES

The efficacy endpoints are:

- to evaluate whether the incidence of preoperative microembolic signals (MES) is reduced in patients with symptomatic carotid artery stenosis who have been treated with Revacept plus antiplatelet therapy (aspirin or clopidogrel) versus antiplatelet therapy alone (placebo) prior to carotid endarterectomy (CEA) or carotid artery stenting. MES will be assessed by transcranial Doppler (TCD) examination (before and after treatment).
- Rate of MES per hour (before and after treatment)
- Assessment of neurological status (NIH Stroke Scale)
- Cerebral lesion analysis by DWI-NMR and correlation to neurological status (before and after treatment and CEA or stenting)
- Clinical endpoints will be summarised cumulatively i.e. before treatment, one and three days after treatment, at 3 months and at 12 months. The following endpoints will be recorded:
  - Rate of all cause death
  - Rate of stroke-related death
  - Any TIA or stroke including haemorrhagic stroke
- Assessment of cardiovascular outcome including myocardial infarction and re-intervention up to 3 and 12 months
- Combined clinical endpoints for ischemic events (myocardial infarction and ischemic stroke/TIA) and rate of rescue medication (additional anti-platelet co-medication) during the study

Safety will be summarised by treatment group and include the following:

- Vital signs
- ECG parameters
- Anti-drug antibody titres
- Reporting AEs including wound healing complications, laboratory abnormalities and use of concomitant medication
- Haemostasis will be closely monitored by assessing:
  - laboratory parameters indicating thrombocytopenia and bleeding according to the RELY study group criteria
  - where feasible: in vitro platelet function with collagen, TRAP and ADP-mediated platelet aggregation and in vitro bleeding time by PFA-100 / PFA-200

### 3. STUDY DESIGN

Number of centers:	16 active centers (planned $\geq 3$ centers)
Randomized:	Yes
Blinded:	double-blinded
Design:	Phase II study
Dosing:	Dose-finding - 2 doses
Placebo controlled:	Yes
Strata:	Yes 

- anti-platelet therapy prior to screening

- statin therapy prior to screening

- degree of carotid stenosis

Treatments:	Placebo 40 mg Revacept 120 mg Revacept

#### 3.1 Assigning Subjects to Treatment Groups / Randomisation

Eligible subjects were randomised to one of three treatment groups.

The first 10 patients were treated sequentially, e.g. only one patient was randomised at a time. The next patient was randomised only once the first patient has completed visit 5 and and not suffered a suspected unexpected serious adverse event. Once the first 10 patients have completed the sequential phase and the DSMB has recommended continuing the trial, parallel recruitment was started (see also section 1.3 of the protocol).

The study was conducted at 16 study centres which were planned to screen and recruit 150 eligible patients. During the recruitment period, each study centre was expected to provide the capacity and willingness to recruit at least 20 patients. There was a competitive recruitment of patients, which means that some hospitals were to enrol more than 20 patients and some less.

However, if a study centre randomised less than 3 patients, further recruitment of patients may have been stopped because the quality of a study was dependent on the number of patients per centre. Very few patients in a centre might be related to a higher rate of missing data or patient visits and a higher withdrawal rate.

Patients were assigned to a treatment group by web-based online randomisation. Each patient was allocated to one of the three treatment arms using a minimised randomisation method in order to balance potential prognostic factors between individual treatment arms. The following stratification factors had impact on treatment allocation:

- (1) Patient has received anti-platelet therapy with aspirin or clopidogrel prior to screening (Yes/No)
- (2) Patient has received statin therapy prior to screening (Yes/No)
- (3) Degree of carotid stenosis (50 - 70% / > 70%)

## **3.2 Blinding**

Emergency unblinding is performed using the web-based online randomisation tool. The Investigator should ensure that the code is broken only in accordance with the protocol. For unblinding, the Investigator should note the date, time and reason for unblinding in the patient notes and promptly inform the Monitor or Sponsor and the Coordinating Investigator of any premature unblinding (e.g. accidental unblinding, unblinding due to a serious adverse event) of the investigational product(s).

## **3.3 Sample size**

Primary sample size estimation was conducted based on the CARESS study results (Markus et al., 2005). 50 patients should be allocated to each treatment arm. Due to low incidence of MES (high screening failure rates) study design was changed to exploratory study (Version 8 of the study protocol).

## 4. STUDY VARIABLES

### 4.1 Efficacy endpoints

- to evaluate whether the incidence of preoperative microembolic signals (MES) is reduced in patients with symptomatic carotid artery stenosis who have been treated with Revacept plus antiplatelet therapy (aspirin or clopidogrel) versus antiplatelet therapy alone (placebo) prior to carotid endarterectomy (CEA) or carotid artery stenting.  
MES was assessed by transcranial Doppler (TCD) examination (before and after treatment).
- Rate of MES per hour (before and after treatment)
- Assessment of neurological status (NIH Stroke Scale)
- Cerebral lesion analysis by DWI-NMR and correlation to neurological status (before and after treatment and CEA or stenting)
- Clinical endpoints will be summarised cumulatively i.e. before treatment, one and three days after treatment, at 3 months and at 12 months. The following endpoints will be recorded:
  - Rate of all cause death
  - Rate of stroke-related death
  - Any TIA or stroke including haemorrhagic stroke
- Assessment of cardiovascular outcome including myocardial infarction and re-intervention up to 3 and 12 months
- Combined clinical endpoints for ischemic events (myocardial infarction and ischemic stroke/TIA) and rate of rescue medication (additional anti-platelet co-medication) during the study

### 4.2 Safety endpoints:

- Vital signs
- ECG parameters
- Anti-drug antibody titres
- Reporting AEs including wound healing complications, laboratory abnormalities and use of concomitant medication
- Haemostasis will be closely monitored by assessing:
  - laboratory parameters indicating thrombocytopenia and bleeding according to the RELY study group criteria
  - where feasible: in vitro platelet function with collagen, TRAP and ADP-mediated platelet aggregation and in vitro bleeding time by PFA-100 / PFA-200

## 5. STUDY PLAN

The study schedule was as follows:

- Visit 1: Screening  
Unsuccessfully screened subjects may have been re-screened if necessary. Visit 1 procedures should have been performed within 24 hours.
- Randomisation  
Once all screening examination results were available and indicated that the patient was eligible for the study, patients were allocated to a treatment arm by stratified randomization.
- Visit 2: Treatment  
Pharmacokinetic blood sampling (for approximately 20 % of patients)
  - t0 prior to IMP administration
  - t0.5h 30 mins ( $\pm$  5 mins) after start of IMP infusion
  - t6h 6 h ( $\pm$  1 hr) after start of IMP infusionAdministration of study medication was performed by intravenous infusion for 20 minutes.
- Visit 3: 24 hrs after treatment (between 2 hrs and 46 hrs after treatment)  
Pharmacokinetic blood sampling (for approximately 20 % of patients)
  - t24h 24 hours ( $\pm$  4 hrs) after start of IMP infusion
- Visit 4: CEA / intervention (3 days after treatment, -69 hrs / + 5 days)  
Pharmacokinetic blood sampling (for approximately 20 % of patients)
  - t3d 3 days ( $\pm$  48 hrs) after start of IMP infusion
- Visit 5: 24 hrs after CEA or other intervention ( $\pm$  24 hrs)
- Visit 6: follow up 3 months after treatment ( $\pm$  1 month)  
Pharmacokinetic blood sampling (for approximately 20 % of patients)
  - t3m 3 months ( $\pm$  1 month) after IMP infusion
- Visit 7: 12 months follow up ( $\pm$  1 month)  
Assessment of clinical outcome

Procedure	Visit	Screening	Randomisation	Treatment (T)	T +24 hrs (±22 hrs)	CEA T + 3 d (-69 hrs/+5d)	CEA + 24 hrs (±12 hrs)	Follow Up		
		1		2	3	4	5	T+ 3 m (±1 m)	T + 12 m (±1 m)	
Informed consent		x	x							
Randomisation										
Study medication (Revacept or placebo)				x						
CEA or other intervention							x r			
CEA / intervention outcome								x r		
Assessment of wound healing								x r	x	
Complications										
Anamnesis		x								
Concomitant medication		x			x	x	x	x	x	
Physical examination		x r			x	x	x r	x r	x	
Adverse events					x	x	x	x	x	
MRS, Barthel Index					x r				x	
NIH Stroke Scale					x r			x r	x	
Clinical outcome									x	x
TCD		x				x				
Electrocardiogram		x r				x		x r	x	
DWI-NMR		X a,r						x		
Laboratory Tests	Biochemistry	x r				x r		x r	x	
	Haematology / Bleeding	x r				x r		x r	x	
	Coagulation	x r				x r		x r	x	
	Urinalysis	x r			x r		x r	x		
	In vitro bleeding time (PFA100) and aggregation				X*	X*	X*		X*	
	Pregnancy test	x								
	Pharmacokinetics (selected patients)				x b	x c	x c		x e	
	Anti-drug antibodies				x				x	

r routine assessment / blood sampling

\* where feasible

a eligible patients only

b drawing times: t0 prior to IMP administration, t 0.5h 30 mins (±5 mins) after start of IMP infusion, t 6h: 6 h (±1 hr) after start of IMP infusion

c drawing time: t24h (±4 hrs) after start of IMP infusion

d drawing time: t3d (±48hrs) after start of IMP infusion

e drawing time: t3m (±1month) after start of IMP infusion

## **6. ANALYSIS SETS**

### **6.1 Safety Set**

All Subjects who have received study medication and have had one contact with the Investigator afterwards will be analysed for safety.

### **6.2 Full Analysis Set**

For efficacy, all subjects who have had at least one dose of medication will be included in the ITT analysis. The ITT analysis is defined as the first line efficacy analysis.

### **6.3 Per Protocol Set**

The PP population includes all subjects who are eligible for ITT evaluation and who, in addition, do not show major protocol deviations.

Exclusion criteria for the study are:

- Extracranial carotid artery stenosis (diagnosed by vascular duplex ultrasound peak flow or angiography) - Lesions with < 50 % stenosis according to European Carotid Surgery Trial (ECST) criteria
- NIHSS score > 18
- Recent intracerebral haemorrhage by X-ray computed tomography (CT) or nuclear magnetic resonance (NMR)
- Cardiac cause of embolisation (atrial fibrillation or other cardiac source e.g. artificial heart valves)
- History of hypersensitivity, contraindication or serious adverse reaction to inhibitors of platelet aggregation, hypersensitivity to related drugs (cross-allergy) or to any of the excipients in the study drug
- History or evidence of thrombocytopenia (<30.000/ $\mu$ l), bleeding diathesis or coagulopathy (pathological international normalised ratio (INR) or activated partial thromboplastin time (aPTT))
- Thrombolysis within the last 48 hours
- Relevant haemorrhagic transformation as determined by CT or anamnesis
- Oral anticoagulation or dual anti-platelet therapy within aspirin or clopidogrel and other P2Y inhibitor at screening (3 days for dipyridamole extended release; 8 hours for tirofiban/Aggrastat)
- Sustained hypertension (systolic BP >179 mmHg or diastolic BP >109 mmHg), hypertensive patients shall be treated in accordance with current guidelines for the management of arterial hypertension
- History of severe systemic disease such as terminal carcinoma, renal failure (or current creatinine >200  $\mu$ mol/l), cirrhosis, severe dementia, or psychosis

Statistical Analysis Plan  
Test product: Revacept  
EudraCT number: 2011-001006-10  
Date 10.06.2019

- Current severe liver dysfunction (transaminase level greater than 5-fold over upper normal range limit)
- Active autoimmune disorder such as systemic lupus erythematosus, rheumatoid arthritis, vasculitis or glomerulonephritis
- Known atrial fibrillation or other clinically significant ECG abnormalities (at present)
- Acoustic window that does not allow for TCD recording
- Subjects who are compulsorily detained for treatment of either a psychiatric or physical illness (e.g. infectious disease)
- Ongoing drug or alcohol abuse

## **7. STATISTICAL CONSIDERATIONS AND DEFINITIONS**

### **7.1 Statistical Software**

All statistical analyses will be performed using the SAS® system (Version 9.4).

### **7.2 Protocol Deviations and Violations/Data Review**

After all queries issued and answered to the extent possible, all medical codes are approved, all SAEs are reconciled, and prior to locking and unblinding the database, a Data Review Meeting will be held. The primary purpose of the meeting will be to resolve outstanding data issues, to examine protocol deviations, to define the analysis sets, and to finalize other statistically related issues.

At the Blinded Data Review Meeting, possible protocol violations will be classified as “major”, “minor”, or “not a protocol violation”. Subjects will be allocated to the individual data sets with regard to the classification of possible protocol violations. The final data sets shall be described in detail in the Blinded Data Review Report.

Major protocol deviations - leading to exclusion from the PP population - are - but not limited to - any of the following conditions:

- Patient did not receive the study medication as planned
- Oral anticoagulation or dual anti-platelet therapy within aspirin or clopidogrel and other P2Y inhibitors at screening (3 days for dipyridamole extended release; 8 hours for tirofiban/Aggrastat)
- Other concomitant medication prohibited according to the exclusion / inclusion criteria
- Systolic blood pressure >190 mmHg
- Cardiac cause of embolisation (atrial fibrillation or other cardiac cause e.g. artificial heart valves)

Definitions of protocol deviations checked by program are summarized in the following table. This table also includes proposals for classifying protocol deviations as “major”, which are referred to as protocol violations. These should be seriously considered and discussed during the

data review meeting with regard to their impact on statistical analysis and the validity of the results, and the definition of subject populations.

**Table 6-1: Definitions of protocol deviations**

No.	Criterion	Major deviation (violation)
1	Any of the inclusion criteria answered with 'No' Answers will be checked by other sources in the CRF - if possible	Yes or otherwise declared in the definitions in blind review report
2	Any of the exclusion criteria answered with 'Yes' Answers will be checked by other sources in the CRF - if possible	Yes or otherwise declared in the definitions in the blind review report
3	Patient did not receive the study medication as planned	Yes

### 7.3 Handling of Drop-outs or Missing Values

Missing values for the primary analyses at Visit 3 respectively 5 will be imputed by the last observation carried forward approach. This means patients who dropped out before Visit 3 respectively 5 will be counted as non-responder.

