7.2.9. DWI-NMR

The following parameters will be recorded:

- Occurrence of new cerebral lesions from baseline (visit 1) to visit 5
- If possible, number of new cerebral lesions developed between baseline (visit 1) and visit 5

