9. STATISTICAL CONSIDERATIONS

9.1.1. Endpoint Analysis

Endpoint analysis will be performed when 150 patients have completed visit 5 or when advised by the DSMB, whichever occurs earlier. Endpoint analysis includes all data generated from visits 1 to 3.

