Missing values for the primary analyses at Visit 3 will be imputed by the last observation carried forward approach. This means patients who dropped out before Visit 3 will be counted as non-responder.

An additional analysis of the first endpoint will be performed including the factor center as a stratum. Fisher's exact test will be performed for each stratum and meta-analysis approach will be chosen. Centers with less than 3 patients will be combined into a 'small number of patients' combined stratum.

Individual center results will be presented in a graphical overview with risk differences and their confidence intervals.

**In case of heterogeneities in the baseline parameters**, sensitivity analyses will be performed for the first endpoint using Fisher's exact test and by including the respective parameter as a stratum (binary, ordinal or categorical data). For continuous data these data will be transformed into classes before used as stratum.

A meta-analysis approach will be chosen to pool the stratum dependent results and to investigate for heterogeneity in the strata (e.g. Whitehead, 2003).

The following baseline parameters will be used for the analysis of heterogeneity:

- Demographics
  - Age
  - Height
  - Weight
  - Ethnic origin
  - Gender
  - Hormone status
- Anamnesis – Medical history
  - Number of patients with previous diseases and surgeries
- Vital signs
  - systolic and diastolic blood pressure (right and left arm)

- Physical examination
  - Abnormal findings of assessment of heart, lung, abdomen and oedema (Yes/No)

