#### **8.4.4 Cerebral lesion analysis by DWI-NMR 1 day after CEA and correlation to neurological status**

Cerebral lesions: Number of cerebral lesions in perfusion area of carotid artery stenosis assessed at Visit 5 by the central reading lab ([name], Tübingen).

- back
- front right
- front left
- and total

Groups will be compared for

- change of number of DWI lesions V5 compared to V1 (delta number of lesions)
- percent change of number of DWI lesions V5 compared to V1

using ANOVA.

In addition groups will be compared for

- rate of incidence of patients with DWI lesions after treatment (V5)
- rate of incidence of patients with new DWI lesions after treatment (V5)
- rate of patients with DWI lesions in V5 reduced compared to V1

using Fisher's exact test.

Neurological status: Modified Rankin Scale (MRS) assessed at Visit 6:

0	No symptoms at all
1	No significant disability despite symptoms; able to carry out all usual duties and activities
2	Slight disability; unable to carry out all previous activities, but able to look after own affairs without assistance
3	Moderate disability; requiring some help, but able to walk without assistance
4	Moderately severe disability; unable to walk without assistance and unable to attend to own bodily needs without assistance
5	Severe disability; bedridden, incontinent and requiring constant nursing care and attention
6	Dead

The following correlations will be performed by treatment group:

- Cerebral lesions of back area of carotid artery stenosis x MRS
- Cerebral lesions of front right area of carotid artery stenosis x MRS

Statistical Analysis Plan  
Test product: Revacept  
EudraCT number: 2011-001006-10  
Date 10.06.2019

- Cerebral lesions of front left area of carotid artery stenosis x MRS

Correlation analysis will be performed by calculating the Pearson correlation coefficient. In a subgroup analysis, only patients will be compared who did not receive any change in the concomitant medication with anti-platelet activity (=rescue medication) between the initial assessment at V1 and the follow-up investigation at V3 / V5.

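### If SAP 7.3 reaches the Visit 5 DWI endpoints, its two sentences leave a missing Visit 5 scan inconsistently coded or undefined for new DWI lesions

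*SAP*

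**What the plan says.** SAP 7.3 has two sentences. The first sets the method: "Missing values for the primary analyses at Visit 3 respectively 5 will be imputed by the last observation carried forward approach". The second states its consequence: "This means patients who dropped out before Visit 3 respectively 5 will be counted as non-responder".

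SAP 8.4.1 repeats the rule for MES at Visit 3 alone: "Missing values for the primary analyses at Visit 3 will be imputed by the last observation carried forward approach". Response there means MES V3 < MES V1.

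SAP 8.4.4 compares three binary DWI endpoints by Fisher's exact test:
- any lesion: "rate of incidence of patients with DWI lesions after treatment (V5")
- new lesions: "rate of incidence of patients with new DWI lesions after treatment (V5")
- reduction: "rate of patients with DWI lesions in V5 reduced compared to V1"

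It also compares change and percent change in lesion count. It gives no missing-data rule and defines no DWI responder.

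Protocol 7.2.9 lists, as a recorded parameter, "Occurrence of new cerebral lesions from baseline (visit 1) to visit 5". The visit schedules in Protocol 7.1 and SAP 5 place DWI at Visits 1 and 5 only. Protocol 9.3.3 leaves the rules for missing efficacy values to the SAP.

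**The concern.** Section 7.3 treats carry-forward and non-response as the same thing. For MES they are: a Visit 3 value equal to Visit 1 is not a reduction. For an unfavourable event such as a new lesion they need not be, because an unchanged count means no event, which is the good outcome. A patient scanned at Visit 1 who dies before Visit 5 could then count as free of new lesions.

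Missing Visit 5 scans can be expected. The scan is tied to the intervention (12 to 72 hours after it, Protocol 7.1.5), and the schedule marks the intervention as applying only to some patients. Patients who discontinue are invited to go straight to Visit 6 (Protocol 5.2.3), which has no DWI. The full analysis set keeps every treated patient (SAP 6.2), so some code has to be chosen. If the arms lose scans at different rates, the estimated difference in new lesions depends on that choice.

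**Working it through.** **Does 7.3 reach DWI?** Against: it covers primary analyses, no Visit 5 endpoint is called primary, and Protocol 9.1.1 states "Endpoint analysis includes all data generated from visits 1 to 3". For: 8.4.1 already has its own Visit 3 rule, so the mention of Visit 5 in 7.3 must refer to something. The V3 / V5 pairing recurs in SAP 8.4.1, 8.4.2 and 8.4.4, and the only responder-type rates at Visit 5 are the DWI rates in 8.4.4. The reach is a reasonable inference, not a stated rule.

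**Coding if counts are carried forward (V5 = V1).**

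| V1 count | V5 set to | Reduced | New lesion | Any lesion at V5 |
|---|---|---|---|---|
| 0 | 0 | no | no | no |
| 1 | 1 | no | no | yes |
| 3 | 3 | no | no | yes |

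Reduced is always a failure, which agrees with the second sentence of 7.3. New lesion is always the favourable result, which reverses it. Any lesion repeats Visit 1 status.

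**Coding if new-lesion occurrence is recorded directly at Visit 5.** There is no earlier value, so carry-forward is undefined and only the non-responder sentence can apply.

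**Effect on the contrast.** The plan gives no figure to reproduce, and it gives no lesion or loss rates, so these are assumed. Let q be the new-lesion rate, the same in both arms (no true effect), and m_t and m_c the fractions of Visit 5 scans missing on Revacept and placebo. Differences are Revacept minus placebo.

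- Carry-forward: the arm's rate is q(1 - m), so the difference is -q(m_t - m_c).
- Missing counted as a new lesion: the rate is q(1 - m) + m, so the difference is (1 - q)(m_t - m_c).
- Gap between the codings: m_t - m_c, whatever q is.

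| q | Loss, Revacept v placebo | Carry-forward | Missing = new lesion |
|---|---|---|---|
| 0.40 | 10% v 5% | 0.36 - 0.38 = -0.02 | 0.46 - 0.43 = +0.03 |
| 0.40 | 20% v 5% | 0.32 - 0.38 = -0.06 | 0.52 - 0.43 = +0.09 |
| 0.20 | 10% v 5% | 0.18 - 0.19 = -0.01 | 0.28 - 0.24 = +0.04 |
| 0.20 | 20% v 5% | 0.16 - 0.19 = -0.03 | 0.36 - 0.24 = +0.12 |

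Swapping the arms reverses every sign. Equal loss leaves the difference at zero under both codings, though the rates in each arm still move.

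**With a true effect.** Take 30% on Revacept and 40% on placebo, with 10% v 5% loss. Carry-forward gives 0.27 - 0.38 = -0.11; missing as new lesion gives 0.37 - 0.43 = -0.06. The signs agree, and the gap is still 0.05.

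**Nominal tests.** Chance of two-sided Fisher p < 0.05 favouring Revacept under carry-forward, by exact enumeration at 50 v 50 (the planned arm size, SAP 3.3) with q = 0.40 and no true effect: 1.6% at 5% v 5% loss, 2.5% at 10% v 5%, 6.2% at 20% v 5%.

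**The case against.** The strongest reply is that a coherent reading exists. Non-responder fits an improvement endpoint, and at Visit 5 the counterpart of MES V3 < MES V1 is fewer lesions than at Visit 1, where carry-forward and non-response agree. That stands for that endpoint. It leaves new lesions and any lesion without a usable rule, so an edit is needed either way.

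A reader might infer that 7.3 necessarily gives opposite codes for the same patient. The documents do not support that. The conflict requires both that 7.3 extends to DWI and that new lesions are derived from carried-forward counts. Protocol 7.2.9 can equally be read as recording occurrence directly, in which case the rule is undefined rather than reversed.

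A reader might also infer that the choice of coding would flip the sign of the trial's result. The opposite signs in the table follow from assuming no true effect: any unequal loss, however small, then produces them. Nothing in the documents points to 20% v 5% loss in a blinded, single-dose trial, and at 10% v 5% the carry-forward shift is only 1 to 2 points.

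Other points stand in part. Protocol 6.1.8 allows replacement of patients who do not complete Visit 5, so the 50 v 50 model is only an illustration; replaced patients who were treated still appear to belong in the full analysis set. Counts of available data (SAP 7.6) and the raw-data listings by treatment group (SAP 8.7) would show missing scans in part, but neither settles how they are coded. Analysing observed scans alone would drop deaths before Visit 5, so it cannot be the only analysis.

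**Conclusion.** The point holds in conditional form. If 7.3 applies to DWI, a missing Visit 5 scan is coded inconsistently or not at all for new DWI lesions. If it does not apply, 8.4.4 has no rule. Reduced lesions are unaffected, and any lesion at Visit 5 merely inherits Visit 1 status.

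Between arms, the two codings differ by exactly the difference in scan loss: 0.05 and 0.15 in the assumed cases, zero if loss is equal. Lesion and loss rates are assumptions throughout.

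SAP 7.5, 7.6 and 8.4 make every test exploratory, so the harm is an ambiguous or biased estimate and not a false confirmatory claim. Severity is minor to should-fix.

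**What to change.** Before unblinding, for which the blinded data review in SAP 7.2 is a natural point:

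1. In 7.3, limit carry-forward with non-response to the two improvement endpoints: MES V3 < MES V1, and fewer DWI lesions at Visit 5 than at Visit 1.
2. In 8.4.4, for new DWI lesions and for any DWI lesion at Visit 5, do not carry Visit 1 forward. Report the comparison of observed scans together with two bounding analyses in all full-analysis-set patients, counting missing Visit 5 scans (including deaths before Visit 5) first as lesion and then as no lesion. Treat a difference between arms as supported only if its direction is the same in all three.
3. Tabulate missing Visit 5 scans by arm and reason, extending the discontinuation table in SAP 8.1.

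The cost is a few lines of text and a few extra tables. The downsides are wider intervals for the observed-scan comparison and denominators that differ between analyses.
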